4.0 Eligibility

Men with suspected PCa (elevated PSA and/or abnormal DRE) and no prior prostate biopsy will be identified in the UI Health Urology ambulatory clinics by the clinical research coordinator and study investigators.

4.1 Inclusion Criteria

- *Adult men between 18 and 80 years of age*
- *Suspected PCa as defined by elevated PSA ≥ 4 ng/mL and ≤ 20 ng/mL and/or abnormal DRE as determined by a physician*
- *Ability to provide informed consent*

4.2 Exclusion Criteria

- *Prior prostate biopsy*
- *Prior diagnosis of PCa*
- *MRI incompatible implanted medical devices or foreign bodies*
- *Rectal anatomy incompatible with TRUS biopsy*
- *Life expectancy <10 years as determined by the treating urologist*

4.3 Excluded or Vulnerable Populations

- *No vulnerable populations such as minors or incarcerated persons will be included in the study.*

5.0 Subject Enrollment

The study investigators and clinical research coordinator will screen the scheduled encounters at the Urology clinics at UI Health for potentially eligible subjects meeting the inclusion criteria. No advertising materials will be used. No data will be collected from men screened but not enrolled. The clinical research coordinator will discuss the study risks and benefits and obtain informed consent separate from the study investigators to minimize coercion.

5.0 Study Design and Procedures

This will be a single arm prospective clinical trial. Men with clinical suspicion for PCa but no prior prostate biopsy will be enrolled from the UI Health Urology clinics. All eligible men will be screened and enrolled by the clinical research coordinator. Enrolled men will undergo detection protocol MRI at the UIC Advanced Imaging Center (AIC) prior to diagnostic biopsy. The image acquisition parameters are listed in the Appendix 3. The MRI will be processed by the study team and evaluated for areas suspicious for high grade PCa by a board certified clinical radiologist ([name]). Subjects with MRI with no suspicious areas for high grade PCa will undergo SOC 12 core TRUS biopsy. Subjects with MRI suspicious for high grade PCa will have 2-4 biopsies guided toward each suspicious lesion using MRI/TRUS fusion biopsies (maximum of 12 cores). All biopsies will undergo SOC histologic processing and interpretation in pathology. Biopsy results will be communicated to the patients by the Urologist performing the biopsy and all additional management will be SOC. This visit will signify the end of the study. See the study schema in Figure 4.

[figure not shown]

Figure 4: Study schema

The primary outcome will be the rate of detection of high grade PCa on a per-patient and per biopsy core basis. The detection rate will be compared between patients with and without evidence of high grade PCa (GS ≥ 7) based on the detection protocol MRI. Secondarily we will analyze the accuracy of the individual MRI parameters including: T2 imaging, ADC, the SEM parameters (DDC and α), the FROC parameters (μ , Δ , β), the Kurtosis model parameters (D, K), and PI-RADS score.

7.0 Expected Risks/Benefits

The study intervention is the detection protocol MRI and all other aspects of the study are standard of care. The detection protocol MRI is a minimal risk procedure as it does not require intravenous contrast and does not expose the subject to ionizing radiation. Also, in contrast to the aforementioned PRECISION study, patients not found to have suspicion of PCa on the detection protocol MRI will undergo the SOC 12 core TRUS

prostate biopsy thereby resulting in no additional risk of a missed or delayed PCa diagnosis.

The risks of the study are therefore mild anxiety due to the MRI examination itself, and violation of patient privacy due mishandling of protected health information.

Anxiety related to the MRI study, if mild, may be treated with an oral anxiolytic by the primary investigator ([name]) or the patient's primary care physician as is SOC. Severe anxiety precluding MRI without intravenous sedation or general anesthesia will be a reason to exclude a patient from the study. If this severe anxiety is discovered during the MRI, the study and the patient's involvement in the research will be terminated. Health information will be secure in REDCap, principal investigator will allow access to key research personnel only.

The benefits of the study may include: improved detection rate of high grade PCa and lower complication rates compared to standard TRUS 12 core biopsy. If the detection protocol MRI has high negative predictive value, it is possible in the future that unnecessary prostate biopsies could be avoided in men with a negative study, thereby reducing the discomfort and infectious complications of the procedure.

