1.0 Project Summary/Abstract

Currently men with elevated prostate specific antigen (PSA) or abnormal digital rectal examination (DRE) undergo systematic sampling of the prostate with transrectal ultrasound (TRUS)-guided needle biopsies. PSA and DRE have low specificity for prostate cancer (PCa), and TRUS biopsies have an approximately 30% false negative rate. Whether a quantitative detection specific magnetic resonance imaging (MRI) protocol improves PCa detection in biopsy naïve men is not adequately studied.

This pilot study aims to test a novel detection specific MRI protocol which uses image collection and post-processing to assist the radiologist find areas of the prostate with increased suspicion for clinically significant cancer. Men with an MRI negative for cancer will undergo standard of care TRUS biopsies, and men with suspicious MRI lesions (as defined by our preliminary data) will undergo biopsies of these lesions in addition to systematic TRUS biopsies. We will compare the yield of significant PCa between systematic sampling and MRI determined areas of the prostate.

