2.0 Background/Scientific Rationale

While there is concern for over-treatment of prostate cancer (PCa) it remains the 2nd leading cause of cancer death in U.S. men (1). This paradox is due in part to the accuracy limitations of current detection methods of serum prostate specific antigen (PSA) and digital rectal examination (DRE) screening, and the inability of current clinical information to discriminate indolent from aggressive tumors. Clinical patient characteristics including age, race, family history of PCa, DRE, and prior negative prostate biopsy history have been combined into a predictive calculator to guide biopsy decisions(2). Men found to have adequate suspicion for PCa require a tissue diagnosis. Standard PCa detection relies on 12-core transrectal ultrasound (TRUS) guided biopsy that samples anatomic zones of the prostate gland. Approximately 35% of men undergoing immediate radical prostatectomy (RP) for low grade PCa on standard biopsy will be found to have higher grade tumors in the pathologic specimen(3). Furthermore, between 30-38% of men with clinical suspicion for PCa and a negative standard biopsy will be diagnosed with PCa on re-biopsy(4). Finally, TRUS biopsy is an invasive procedure with a rate of sepsis as high as 2%, and this risk is proportional to the number of biopsy cores sampled(5). With a more precise method for early detection of the most aggressive tumors, men with indolent PCa could be spared treatment with its associated cost and morbidities and instead be managed conservatively with active surveillance (AS), while those with potentially lethal disease could be expediently referred for radiation or surgery with curative intent.

Improved PCa detection may be particularly important for African American (AA) men, who are almost twice as likely to die from PCa as white men(1). A recent study of men with very low risk PCa based on clinical information who underwent immediate RP found that AA men were more likely to have adverse RP pathology and anteriorly located tumors not reached with standard TRUS prostate biopsies(6). In addition, two series of men selected for AS based on standard clinical information reported that AA men progressed to treatment faster than white men(7, 8). These data have questioned the safety of managing AA men with AS without more accurate risk stratification tools such as imaging. At UIC, over 60% of PCa cases diagnosed are in AA men.

[figure not shown]

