Standard TRUS imaging does not provide enough resolution to localize most PCa, much less provide information about its aggressiveness. One promising approach to improve PCa detection and risk stratification is through advanced imaging such as magnetic resonance imaging (MRI). In this setting an ideal imaging study would differentiate aggressive PCa from indolent PCa and benign processes such as hyperplasia (BPH) or inflammation as well as localize the aggressive PCa to reduce biopsy sampling error. Currently in the US, prostate mpMRI is approved for : 1) men with continued suspicion for PCa but negative TRUS biopsy or 2) for staging of known high risk PCa for treatment planning. The images from the mpMRI can be used for

[figure not shown]
targeted biopsies using TRUS/mpMRI imaging fusion to improve PCa detection(9). As such, there is interest in using mpMRI as a confirmatory test in men with elevated PSA and prior to the first biopsy to improve biopsy accuracy and potentially obviate the need for unnecessary “random” biopsies. A landmark study conducted in Europe, the PRECISION trial, recently reported that TRUS/mpMRI fusion biopsies in biopsy naive men with suspected PCa resulted in an increase in the absolute detection of clinically significant PCa of 12% in men randomized to mpMRI, despite 28% of the men in this group avoiding biopsy due to a negative study(10). These data are certainly compelling, but have yet to be replicated in a US population, and particularly in a high-risk group such as AA men. The implications in the US are significant as approximately 1 million TRUS biopsies are performed annually for known or suspected PCa(11).

While MRI protocols are variable and evolving, the current recommended standard is combining T2-weighted anatomical imaging (T2WI) with two functional MRI techniques, typically diffusion-weighted images (DWI) and dynamic contrast enhanced images (DCE), together to create a multi-parameter MRI (mpMRI) study. A radiologist reviews the imaging and assigns a semi-qualitative suspicion of high grade PCa on a 1-5 Likert scale. This score, called the prostate imaging reporting and data system (PI-RADS), is an attempt to standardize mpMRI assessment and guide clinical management(12).

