3.0 Objectives/Aims

This study aims to determine whether a detection specific MRI protocol with quantitative image analysis can improve high grade PCa detection in men with clinical suspicion and no prior biopsy.

Aim 1: Design a PCa detection specific MRI protocol which will facilitate quantitative image analysis and reduce study time by ~50%

Current prostate mpMRI protocols include image sequences and fields of view outside of the prostate gland and its immediate surrounding that are not useful for PCa detection. We will create a detection specific MRI protocol featuring: smaller fields of view zoomed to the prostate, T2 weighted imaging at multiple echo times, chemical exchange saturation transfer imaging (CEST), and DWI at higher b values (up to 4000) that will allow for quantitative prediction of high grade PCa. The exact imaging acquisition parameters can be found in Appendix 3. We expect this MRI protocol to

reduce study (acquisition) time from approximately 45 minutes to 27 minutes, which will potentially lower cost and improve tolerance of the procedure. Significantly, we will omit DCE which will reduce the imaging time, and the risks associated with intravenous contrast including systemic fibrosis, and patient discomfort.

Aim 2: Determine the accuracy of the novel MRI protocol for detection of high grade PCa

50 men with clinical suspicion of PCa (elevated PSA and/or abnormal DRE) will be enrolled into a prospective protocol and will undergo detection protocol MRI described in Aim 1. Quantitative image analyses will be performed to generate SEM maps of DWI. Areas of suspicion for high grade PCa (GS ≥ 7) will be targeted for biopsy. Men with MRI with no areas of suspicion for high grade PCa will undergo standard of care 12 core TRUS biopsy. The primary endpoint will be the rate of detection of high grade PCa on the per patient and per biopsy core basis. Men with biopsy pathology negative for PCa will undergo standard of care (SOC) continued monitoring.

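### Section 7.0 argues its claim of no added risk of a missed or delayed diagnosis only for MRI-negative men, while the protocol describes the biopsy of MRI-positive men in two conflicting ways

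*Combined protocol and SAP*

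**What the plan says.** Section 7.0 (Expected Risks/Benefits) starts from the premise that "The study intervention is the detection protocol MRI and all other aspects of the study are standard of care". It then contrasts the study with PRECISION: here "patients not found to have suspicion of PCa on the detection protocol MRI will undergo the SOC 12 core TRUS" biopsy, "thereby resulting in no additional risk of a missed or delayed PCa diagnosis". The next sentence derives the risk list from this, namely mild anxiety from the scan and mishandling of health information. The sampling of MRI-positive men is not mentioned. Among the possible benefits the section names fewer complications than with the 12-core biopsy.

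The biopsy itself is described in six other places:

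- Section 2.0 defines usual practice: "Standard PCa detection relies on 12-core transrectal ultrasound (TRUS) guided biopsy". It also puts the sepsis rate of TRUS biopsy at up to 2% and says that this risk rises in proportion to the cores taken.
- Section 3.0, Aim 2: "Areas of suspicion for high grade PCa (GS ≥ 7) will be targeted for biopsy". The 12-core biopsy is assigned to men without such areas.
- Section 5.0 (Study Design and Procedures): "Subjects with MRI suspicious for high grade PCa will have 2-4 biopsies guided toward each suspicious lesion using MRI/TRUS fusion biopsies", with a maximum of 12 cores. No systematic cores are mentioned.
- Section 8.0 records the biopsy type in one of two categories, standard or targeted.
- Section 12.0 compares 12-core biopsy in MRI-negative men with targeted biopsy in MRI-positive men.
- Section 1.0 says that men with suspicious lesions "will undergo biopsies of these lesions in addition to systematic TRUS biopsies".

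**The concern.** The study MRI sorts men into two groups, and the risk argument covers only one of them. For the other group, the procedures sections describe cores at the lesions and nothing else. If that is what happens, the study changes both the number and the placement of cores in the men under most suspicion. Disease outside a target that a 12-core biopsy might have sampled could then go unsampled because of the study MRI. A review board reading Section 7.0 would conclude that the study leaves diagnostic sampling unchanged. That conclusion needs an argument for MRI-positive men, and the section offers none.

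**Working it through.** The plan gives no figure for this risk, so there is none to reproduce. The check sets the sections side by side and counts cores.

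**Step 1: the inference in Section 7.0.** The stated reason is that MRI-negative men still have the 12-core biopsy. From this the section moves to no added risk of a missed or delayed diagnosis, and then to a risk list for the whole study. The reason supports the conclusion for MRI-negative men. It is silent on MRI-positive men.

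**Step 2: cores for an MRI-positive man under Section 5.0 (Study Design and Procedures).** Cores = 2 to 4 × number of lesions, with a maximum of 12.

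- 1 lesion: 2 to 4
- 2 lesions: 4 to 8
- 3 lesions: 6 to 12
- 4 lesions: 8 to 16, limited to 12

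All of these cores are aimed at lesions. The two-category field in Section 8.0 and the either/or comparison in Section 12.0 fit this description. So does the expected fall in complications, given that Section 2.0 links sepsis to core number. On this reading a man with one lesion has 2-4 targeted cores where Section 2.0's usual practice is 12 across anatomic zones. Both the no-added-risk statement and the premise that everything except the MRI is standard of care then lack support for him.

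**Step 3: cores under Section 1.0.** That section does not say how many systematic cores are meant. Assume the 12 that Section 2.0 calls standard.

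- 1 lesion: 12 + 2 = 14 to 12 + 4 = 16

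If the maximum of 12 covers the whole session, 14 already exceeds it, and Sections 1.0 and 5.0 cannot both be followed. If the maximum covers targeted cores only, they can. The no-added-risk statement is then easier to support, because these men keep the systematic biopsy. But core number rises by a factor of 14/12 = 1.17 to 16/12 = 1.33 over the standard biopsy. If sepsis risk is proportional to cores, as Section 2.0 says, it rises by the same factor. A risk list of anxiety and privacy would then be incomplete, and a benefit of fewer complications than with 12 cores would not follow for these men.

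**Step 4: the size of any missed disease.** This would need the proportion of MRI-positive men with high grade disease only outside the targets, and the share of those that a 12-core biopsy would find. The documents do not give the proportion for this or any other MRI protocol.

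**The case against.** The sentence on missed diagnosis can be read narrowly. It opens by contrast with PRECISION, where Section 2.0 says that 28% of the MRI group avoided biopsy after a negative study. It answers that specific worry, and for MRI-negative men it is right. This stands. The study-wide claim comes from what surrounds it: the premise that only the MRI departs from standard care, and the risk list drawn as a consequence.

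It is also fair to say that replacement of the 12-core biopsy is inferred. No section says that targeted cores are taken instead of systematic ones. The maximum of 12 can be read as applying to fusion cores alone. The one explicit sentence on whether MRI-positive men also have systematic cores is in Section 1.0, and it says that they do. The schema in Figure 4 might settle the matter but could not be seen. So the documents show a contradiction, with targeted-only sampling as the more natural reading of the procedures sections. They do not establish what will be done.

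Three stronger readings are tempting, and the documents do not support them.

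- A reader might infer that the study will miss cancers, and try to count them: 50 × (1 − 0.28) = 36 MRI-positive men, times some rate of disease outside targets. The 28% belongs to a different MRI and population, and the rate would be invented. Such a count would also ignore the roughly 30% false negative rate that Section 1.0 gives for TRUS biopsy. It would ignore too the 12% absolute gain in detecting significant cancer that Section 2.0 reports for the MRI group in PRECISION. Net detection could rise.
- A reader might infer that targeted biopsy falls outside standard care from the list of imaging uses ("Currently in the US, prostate mpMRI is approved for : 1) men with continued suspicion for PCa but negative TRUS biopsy" and staging of known high risk disease). What imaging is approved for is a different matter from standard biopsy technique. Section 2.0's definition of standard detection is the sounder basis.
- A reader might infer that participants are misinformed. The consent text was not available, so this cannot be checked.

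**Conclusion.** The point holds as a defect in the reasoning of Section 7.0 combined with a contradiction between sections. On the more natural reading of Sections 3.0, 5.0 (Study Design and Procedures), 8.0 and 12.0, the no-added-risk and standard-of-care statements are unsupported for MRI-positive men. Under Section 1.0 they are easier to support, but the risk list and the complication benefit then need revising. Some part of Section 7.0 therefore has to change under either scheme.

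The size can be stated only in cores. A man with one lesion has 2-4 on one description and 14-16 on the other, the latter assuming a systematic set of 12. No count of missed cancers should be given, because neither the magnitude nor the net direction of any added diagnostic risk can be derived from the documents. The correction still matters, since this is a safety statement about the men with suspicious scans.

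**What to change.** State one biopsy scheme for MRI-positive men, and use it in Sections 1.0, 3.0, 5.0 (Study Design and Procedures), 7.0, 8.0 and 12.0. The text should say whether systematic cores are taken and whether the maximum of 12 covers the session or the targeted cores only. Which scheme applies is for the investigators to decide.

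Then make four statements in Section 7.0 agree with it: no added risk of a missed or delayed diagnosis, standard of care apart from the MRI, the list of risks, and the lower complication rate. If the chosen scheme does not support the first of these for MRI-positive men, limit it to MRI-negative men and disclose that disease outside the targeted areas may be missed. Any consent text that rests on Section 7.0 should be checked and changed in the same way.

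The cost is a protocol amendment, possibly with consent wording, and a risk statement that may read less favourably.

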8.0 Data Collection and Management Procedures

To meet the study goals, clinical, imaging, and pathologic data will be collected prospectively. The co-investigators and other key personnel will have access to the identified data while the subject is on study. A REDCap database will be used to record all of the baseline and clinical data for each subject including: age (continuous in years), self reported race (white, black, Hispanic, other), family history of prostate cancer (positive or negative), serum PSA (continuous, in ng/mL), International Prostate Symptoms Score (IPSS: continuous), Sexual Health Inventory for Men score (SHIM: continuous). All source MRI images from the scanner as well as post-processed images will be collected in Digital Imaging and Communications in Medicine (DICOM) format. Image data will be stored on a password protected server and physically transported from the scanner to the post-processing workstation and to the radiologist workstation using an encrypted flash drive. Data from interpretation of the MRI images to be stored in REDCap will include: PI-RADS score (ordinal), number of lesions (ordinal), and the lesion mean, median, minimum and maximum for each quantitative MRI parameter if applicable. In addition, if applicable each lesion will be outlined on the T2 weighted image series by the radiologist for use at the time of biopsy. At the time of biopsy the prostate volume (continuous, cubic centimeters), type of biopsy (standard or targeted), and number of biopsy cores obtained (ordinal) will be entered in REDCap. Pathology data to be collected and stored in REDCap includes: presence of any carcinoma (Boolean), number of biopsy cores involved with carcinoma (ordinal), location of positive biopsy cores (ordinal lesion number), and maximum GS of biopsies (categorical:

6,7,8,9, or 10). At the biopsy results visit, biopsy complications will be recorded in REDCap: hematuria persisting greater than 72 hours (boolean), urinary retention (boolean), infectious complication (boolean). All data will be de-identified for each subject after study visit #4 when the biopsy results are known. We anticipate approximately 1 year to meet the enrollment goals. At this time, a 3 month period for data analysis of the primary outcome is anticipated. After this time, the de-identified data will be stored by the primary investigator ([name]) for potential use for secondary retrospective studies under separate IRB approval. See Appendix 4 for the data flow diagram.

